5.1.3 Statistical Methods for Exploratory Objective(s)

Analyses will be performed on the Randomized participants:

• GMT of NAb levels against FV infection (dengue and Zika) for each vaccine group at baseline

5.2 Analysis Sets

Population	Description
Randomized	All participants with data in the CRF.
Full analysis set (FAS)	Subset of randomized participants who received at least 1 dose of the study vaccine or control vaccine and had a valid post-vaccination blood sample result.
	Participants will be analyzed according to the intervention to which they were randomized.
Safety Analysis Set (SafAS)	Participants who have received at least 1 dose of the study vaccines. All participants will have their safety analyzed according to the vaccine they actually received.
	Safety data recorded for a vaccine received out of the protocol design will be excluded from the analysis (and listed separately).
Per-protocol analysis set (PPAS)	Subset of the FAS. Participants presenting with at least one of the following relevant protocol deviations will be excluded from the PPAS:
	Participant is not YF-naïve
	• Participant did not meet all protocol-specified inclusion criteria or met at least one of the protocol-specified exclusion criteria.
	• Participant received a vaccine other than the one that he / she was randomized to receive.
	 Preparation and / or administration of vaccine was not done as per- protocol
	• Non-availability of other critical measurements for the primary analysis:
	• Baseline serology sample was not collected in the protocol-specified time window or the serology sample was not drawn

The following populations are defined:

	• Participant did not provide the post-dose serology sample on Day 29 Visit (D28 after vaccination) in the proper time window or the blood sample was not drawn				
	• Participant received any therapy / medication / vaccine which could inhibit the immune response until the time point considered for the analysis (Day 29, Visit 4).				
	• In addition to the reasons listed above, participants will also be excluded from the PPAS if their baseline or post-vaccination serology on D29 (Visit 4) did not produce a valid test result (ie, results for all antigens are missing or out-of-range).				
	This list may not be exhaustive. The above protocol deviations leading to exclusion from the PPAS may be detailed and completed if necessary, in the SAP following a data review. The PPAS definition will be finalized before the database lock (and code-breaking if applicable)				
	In the event of a local or national immunization program with a eg, pandemic influenza vaccine, any other vaccine as needed, participants who receive 1 or more doses of eg, a pandemic influenza vaccine, or the vaccine listed above at any time during the study will not be withdrawn from the study.				
Subgroup-Per-Protocol	Subset of the PPAS.				
Analysis Set (sub-PPAS)	Participant will be excluded from the sub-PPAS if they did not provide the post-dose serology on Day 29 Visit (D28 after vaccination) in the proper time window of original protocol (D29 +3 days).				

The PPAS will be used for the analysis for the primary objectives. Immunogenicity analyses in secondary objectives will be performed on FAS and a complementary analysis will be provided on sub-PPAS. Demographic and baseline characteristics will be presented on the PPAS and FAS.

The SafAS will be used for the description of clinical safety.

Randomized participants will be used for various standard population tables including duration of the study, disposition of participants and deviations and exploratory objective.

The subset will be used to describe additional neutralizing Ab levels and biological safety parameters in this subset.

5.3 Handling of Missing Data and Outliers

5.3.1 Immunogenicity

No imputation of missing values and no search for outliers will be performed. LLOQ and ULOQ management will be performed as described above.

5.3.2 Safety

Generally, no replacement will be done for Safety Missing Data and Outliers.

5.3.2.1 Immediate

For unsolicited systemic AEs, a missing response to the "Immediate" field is assumed to have occurred after the 30-minute surveillance period and will not be imputed.

5.3.2.2 Causal Relationship

By convention, all events reported at the injection site (either solicited or unsolicited) will be considered as related to the administered product and then referred to as reactions. In a same way, all solicited systemic events pre-listed in the CRF are also considered as related to vaccination and will be considered as reactions.

- For unsolicited systemic AE, missing relationship will be considered as related to study vaccine at the time of analysis.
- If relationship to concomitant vaccine is collected, missing relationship to concomitant vaccine for unsolicited systemic AE will be considered as related to concomitant vaccine.

The missing relationship to study procedures for SAEs will not be imputed.

5.3.2.3 Measurements

For solicited reactions, missing measurements will be handled as described in Section 4.2.2.1.1.

5.3.2.4 Intensity

For solicited reactions, missing intensities will be handled as described in Section 4.2.2.1.1. For unsolicited AEs, missing intensities will remain missing and will not be imputed.

5.3.2.5 Start Date and Stop Date

Missing or partially missing start dates or end dates for unsolicited AEs (including SAEs) will remain missing and not be imputed. If the start date is missing or partially missing, the time of onset will be considered to be missing. Nevertheless, unsolicited AEs with missing time of onset will be included in analyses according to the last vaccination (computed according to the Section 4.2.2.2.3). If either the start date or end date is missing or partially missing, the duration will be considered missing.

Missing or partially missing end dates for ongoing solicited AEs will remain missing and not be imputed.

5.3.2.6 Action Taken

Missing actions taken will remain missing and not be imputed.

5.4 Interim / Preliminary Analysis

Six statistical analyses will be performed on data obtained from all participants.

The first interim analysis will be performed on the immunogenicity results obtained up to D29 visit and safety data obtained up to the 6-month follow-up visit with all available data collected, cleaned and locked. This planned analysis will require the unblinding of data. Once the interim database lock has been conducted, the trial statistician will break the blind and will conduct the statistical analysis.

Then the successive interim analyses will be performed on data collected up to Y1 visit and not yet analyzed, then every year on the data gathered at each yearly visit up to 4 years after YF vaccine administration; these results will be presented in an interim clinical study report (CSR) (immunogenicity data up to D29 and safety data up to M6) or CSR addendum (up to Y4).

Final statistical analysis will be performed at the end of the follow-up (5 years after YF vaccine injection).

5.5 Determination of Sample Size and Power Calculation

The sample size is based on the primary objective and on the safety secondary objectives. A total of 570 participants are expected to be enrolled in the study, using a 2:1 repartition (380 in vYF and 190 in YF-VAX).

Considering a potential attrition rate of \blacksquare %, such sample size would provide 456 evaluable participants with 304 participants enrolled in Group 1 (vYF) and 152 in Group 2 (YF-VAX). This will give > \blacksquare % power (Farrington and Manning formula) to declare the non-inferiority of Group 1 (vYF) versus Group 2 (YF-VAX) based on seroconversion rate of \blacksquare % at D29 after a single dose of the investigational or control vaccine, assuming:

- A one-sided alpha level of 5%
- A non-inferiority margin δ of %

The subset sample size has been arbitrarily set to 90 participants, in which 60 participants will be enrolled in Group 1 and 30 participants will be enrolled in Group 2.

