8.10 Medical Resource Utilization and Health Economics

Medical Resource Utilization and Health Economics parameters are not evaluated in this study.

VYF02

9 Statistical Considerations

All statistical analyses will be performed under the responsibility of the Sponsor's Biostatistics Platform using the Statistical Analysis Software (SAS) at least version 9.4 (SAS Institute, Cary, NC, USA).

A detailed Statistical Analysis Plan (SAP) will be written before the database lock. Based on the protocol, the SAP will describe all analyses to be performed as well as statistical tables, and listings.

9.1 **Statistical Hypotheses**

Primary objective:

A non-inferiority approach will be used to compare the post-vaccination seroconversion rates of vYF and YF-VAX groups in YF-naïve participants. Details on statistical methods are provided in Section 9.4.

Secondary and observational objectives:

No hypotheses will be tested. The analyses will be descriptive.

9.2 **Sample Size Determination**

The sample size is based on the primary objective and on the safety secondary objectives. A total of 570 participants are expected to be enrolled in the study, using a 2:1 repartition (380 in vYF and 190 in YF-VAX).

Considering a potential attrition rate of the , such sample size would provide 456 evaluable
participants with 304 participants enrolled in Group 1 (vYF) and 152 in Group 2 (YF-VAX). This
will give power (Farrington and Manning formula) to declare the non-inferiority of Group
1 (vYF) versus Group 2 (YF-VAX) based on seroconversion rate of at D29 after a single
dose of the investigational or control vaccine, assuming:

A one-sided alpha level of

A non-inferiority margin δ of

The subset sample size has been arbitrarily set to 90 participants, in which 60 participants will be enrolled in Group 1 and 30 participants will be enrolled in Group 2.

9.3 **Populations for Analyses**

The following populations are defined:

Population	Description			
Randomized	All participants with data in the CRF.			

Full analysis set (FAS)	Subset of randomized participants who received at least 1 dose of the study vaccine or control vaccine and had a valid post-vaccination blood sample result.			
	Participants will be analyzed according to the intervention to which they were randomized.			
Safety Analysis Set (SafAS)	Participants who have received at least 1 dose of the study vaccines. All participants will have their safety analyzed according to the vaccine they actually received.			

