5.1 Statistical Methods

5.1.1 Hypotheses and Statistical Methods for Primary Objective(s)

5.1.1.1 Hypotheses

Primary analyses will be performed on the Per-Protocol Analysis Set and on Full Analysis Set.

The objective is to demonstrate that the humoral response (in terms of seroconversion) of vYF (Group 1) is non-inferior to YF-VAX (Group 2) 28 days after a single dose in YF-naïve participants.

The percentages of participants with seroconversion 28 days after vaccination will be used to compare responses between Group 1 and Group 2 with the following hypotheses:

- H0 (Null hypothesis): $p(vYF) p(YF-VAX) \le -\delta$
- H1 (Alternative hypothesis): $p(vYF) p(YF-VAX) > -\delta$

Where δ the non-inferiority margin is set to 5%.

Where p(vYF) and p(YF-VAX) are the proportion of participants with seroconversion. Seroconversion is defined as a fourfold increase in NAb titers as compared to pre-vaccination value.

In the last version of the protocol (version 4 approved on 16^{th} February 2022), the D29 visit is to be performed with a time window of +3 days; a blood sample BL0003 has to be taken at the D29 visit.

However, the timing for the Phase II non-inferiority VYF02 study has been complicated by COVID epidemic waves and vaccination campaigns; when non-COVID work was resuming at Investigational sites, these studies were competing against other studies. As a direct consequence, the enrolments were delayed and longer than expected. Considering that the planned sample size

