was likely to be not reached, the Applicant worked on a mitigation plan based on the number of evaluable subjects (derived from the attrition rate used for the statistical hypotheses) consisting of extending the time window of the D29 post-vaccination visit (initial defined as D29 + 3 days) with a proposal to extend up to D29 + 6 days, as the immune responses should not be impacted by this extension. The analyses with a revised time window for the D29 visit +6days will be presented as the primary analysis of the non-inferiority of the antibody response in terms of seroconversion rates 28 days after vaccine administration of one dose of vYF (administered on D01) compared to the antibody response after one dose of the YF-VAX control vaccine (administered on D01) in YF-naïve participants. If the primary objective is reached, in secondary objective, the originally planned analysis of the non-inferiority of the antibody response on D29 with a time window of +3 days will be presented too on the YF-naïve population only and completed with a descriptive analysis in terms of seroconversion, seroprotection, GMT and GMTR.

The non-inferiority will be demonstrated if the lower limit of the 2-sided 95% confidence interval (CI) of the difference between the 2 percentages is > -5%.

The CI of the difference in percentages will be computed using the Wilson score method without continuity correction as quoted by Newcombe (3) for seroconversion rates.

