5.7 Changes in the Conduct of the Trial or Planned Analyses

In the last version of the protocol (version 4 approved on 16^{th} February 2022), the D29 visit is to be performed with a time window of +3 days; a blood sample BL0003 has to be taken at the D29 visit.

However, the timing for the Phase II non-inferiority VYF02 study has been complicated by COVID epidemic waves and vaccination campaigns; when non-COVID work was resuming at Investigational sites, these studies were competing against other studies. As a direct consequence, the enrolments were delayed and longer than expected. Considering that the planned sample size was likely to be not reached, the Applicant worked on a mitigation plan based on the number of evaluable subjects (derived from the attrition rate used for the statistical hypotheses) consisting of extending the time window of the D29 post-vaccination visit (initial defined as D29 + 3 days) with a proposal to extend up to D29 + 6 days, as the immune responses should not be impacted by this extension. The analyses with a revised time window for the D29 visit +6days will be presented as the primary analysis of the non-inferiority of the antibody response in terms of seroconversion rates 28 days after vaccine administration of one dose of vYF (administered on D01) compared to the antibody response after one dose of the YF-VAX control vaccine (administered on D01) in YF-naïve participants. If the primary objective is reached, in secondary objective, the originally planned analysis of the non-inferiority of the antibody response on D29 with a time window of +3 days will be presented too and completed with a descriptive analysis in terms of seroconversion, seroprotection GMT and GMTR.

Moreover, by contrast to the analyses defined in the protocol, the first interim analysis will be performed on safety and immunogenicity data gathered from D01 to D29 (instead of M6 for safety data).

6 References List

- Eduardo J. M. Nascimento, Matthew I. Bonaparte, Ping Luo, Timothy S. Vincent, Branda Hu, James K. George, Germán Áñez, Fernando Noriega, Lingyi Zheng and James W. Huleatt. "Use of a Blockade-of-Binding ELISA and Microneutralization Assay to Evaluate Zika Virus Serostatus in Dengue-Endemic Areas" Am. J. Trop. Med. Hyg., 101:708-715, 2019.
- 2 Newcombe R.G., Two-sided confidence intervals for the single proportion: comparison of seven methods, Statistics in Medicine, (1998) 17, 857-872

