Table 7.10: Abnormality and/or intensity for Biochemistry parameters measurements at D01and D11 – Subset
Table 7.11: Abnormality and/or intensity for Hematology parameters measurements at D01and D11 - Subset52
Table 7.12: Evolution of the intensity for Biochemistry parameters after vaccine injection - Subset 54
Table 7.13: Evolution of the intensity for Hematology parameters after vaccine injection – Subset

List of Figures

Figure 7.1: Reverse cumulative distribution curves for YF virus at each timepoint in participants with YF immune status at baseline - Microneutralization assays - Full Analysis Set	56
Figure 7.2: Reverse cumulative distribution curves for YF virus at each timepoint in participants with YF naive status at baseline - Microneutralization assays - Full Analysis Set	57
Figure 7.3: Reverse cumulative distribution curves for YF virus at each timepoint in participants with FV immune status at baseline - Microneutralization assays - Full Analysis Set	57
Figure 7.4: Reverse cumulative distribution curves for YF virus at each timepoint in participants with FV naive status at baseline - Microneutralization assays - Full Analysis Set:	57

 Table 7.1: Non-inferiority of the percentage of participants achieving seroconversion 28 days after one dose yellow fever vaccination in YF-naïve participants - Microneutralization assays - Per-Protocol Analysis Set

	vYFv			YF-VAX				
(N=xxx)			(N=xxx)			vYF – YF	Non-inferiority	
	Seroconversion rate			Seroconversion				
n/M	(%)	95% CI	n/M	rate (%)	95% CI	Difference (%)	95% CI	
###/###	##.#	(##.#; ##.#)	###/###	## . #	(##.#; ##.#)	##.#	(##.#, ##.#)	Yes/No

n: Number of participant s who achieve a yellow fever vaccination seroconversion.

M: Number of participant s with available data for the endpoint.

Seroconversion: for a participant with a fourfold increase in NAb titers as compared to the pre-vaccination value

The non-inferiority will be demonstrated if the lower limit of the 2-sided 95% CI is > -5%.

YF status			v' (N=	YF =###)		YF-V (N=#	AX ##)
	Time point/ratio	Μ	GM	(95% CI)	М	GM	(95% CI)
Immune	V01 (Pre-inj)	###	###.#	(###.#; ###.#)	###	###.#	(###.#; ###.#)
	V02 (V01+10d)*	###	###.#	(###.#; ###.#)	###	###.#	(###.#; ###.#)
	V04 (V01+28d)	###	###.#	(###.#; ###.#)	###	###.#	(###.#; ###.#)
	V05 (V01+6M)	###	###.#	(###.#; ###.#)	###	###.#	(###.#; ###.#)
	V06 (V01+1Y)	###	###.#	(###.#; ###.#)	###	###.#	(###.#; ###.#)
	V07 (V01+2Y)	###	###.#	(###.#; ###.#)	###	###.#	(###.#; ###.#)

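### SAP 5.5 bases the power on a one-sided 5% alpha, but non-inferiority is decided on a two-sided 95% CI, which is a one-sided 2.5% test

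*SAP*

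**What the plan says.** **Planning.** SAP 5.5 plans 570 participants in a 2:1 ratio (380 and 190), of whom 456 are expected to be evaluable (304 and 152). It claims a power above a blacked-out percentage by the Farrington-Manning formula, at a blacked-out seroconversion rate. The listed assumption on error rate is "A one-sided alpha level of 5"%. Protocol 9.2 has the same sentence, "A one-sided alpha level of", but with the figure removed.

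**Decision.** SAP 5.1.1.1 declares non-inferiority "if the lower limit of the 2-sided 95% confidence interval (CI) of the difference between the 2 percentages is > -5"%. The footnote to the SAP Table 7.1 shell repeats this: "The non-inferiority will be demonstrated if the lower limit of the 2-sided 95% CI is > -5"%. Protocol 9.4.1 gives the same rule. The interval is the "Wilson score method without continuity correction as quoted by Newcombe".

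**Margin.** The figure is missing from the sample-size section, but SAP 5.1.1.1 says that "the non-inferiority margin is set to 5"%, and Protocol 9.4.1 agrees.

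Neither document mentions a 90% interval or explains why planning and testing would use different levels.

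**The concern.** Requiring the lower limit of a two-sided 95% interval to exceed −5% is a one-sided test at a nominal 2.5%. A calculation at one-sided 5% describes a different and easier test, the one that would use a two-sided 90% interval. With the same formula and numbers of participants, halving alpha always lowers power, so the direction of the discrepancy is certain even though the stated power is hidden.

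The power statement is the reason given for the size of the trial's one confirmatory comparison. If the result is narrow or fails, readers will judge it against that power. A figure that belongs to another test would mislead them about how likely a truly equivalent vaccine was to miss the margin.

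**Working it through.** **Inputs**
- Evaluable numbers: n1 = 304 (vYF), n2 = 152 (YF-VAX), from SAP 5.5.
- Margin: δ = 0.05, from SAP 5.1.1.1 and Protocol 9.4.1.
- Alpha: 0.05 in SAP 5.5; 0.025 implied by the decision rule.
- True seroconversion rate: blacked out. Assumed equal in both arms and varied from 95% to 99%.

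**What can be reproduced.** 304/380 = 152/190 = 456/570 = 0.80, so the evaluable numbers are consistent with 20% attrition. The power itself cannot be reproduced, because both its value and the assumed rate are hidden.

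**Step 1: Farrington-Manning power**

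Power = Φ[(δ − z·s0)/s1], where
- s1 = √[p(1−p)(1/304 + 1/152)];
- s0 = √[q1(1−q1)/304 + q2(1−q2)/152];
- q1 and q2 are the maximum-likelihood rates restricted to q1 − q2 = −0.05.

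Worked example at p = 0.97: q1 = 0.93586, q2 = 0.98586, s0 = 0.017005, s1 = 0.016946.
- One-sided 5%: (0.05 − 1.645 × 0.017005)/0.016946 = 1.300, power 90.3%.
- One-sided 2.5%: (0.05 − 1.960 × 0.017005)/0.016946 = 0.984, power 83.7%.

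**Step 2: exact power of the planned rule**

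The Newcombe lower limit is L = (p̂1 − p̂2) − √[(p̂1 − l1)² + (u2 − p̂2)²], where l1 is the Wilson lower limit for vYF and u2 the Wilson upper limit for YF-VAX. Power is the sum of the binomial probabilities of all pairs of counts for which L > −0.05. It was computed for the planned 95% interval and, for comparison, for a 90% interval.

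| True rate, both arms | FM, one-sided 5% | FM, one-sided 2.5% | Newcombe 90% CI, exact | Newcombe 95% CI (planned), exact | FM 5% minus planned rule |
|---|---|---|---|---|---|
| 95% | 77.5 | 67.6 | 79.3 | 70.2 | 7.3 |
| 96% | 83.8 | 75.3 | 86.4 | 79.0 | 4.8 |
| 97% | 90.3 | 83.7 | 93.3 | 88.1 | 2.2 |
| 98% | 96.2 | 92.4 | 98.1 | 96.0 | 0.2 |
| 99% | 99.7 | 99.0 | 99.9 | 99.7 | 0.0 |

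Powers are in %. The last column is the difference of the rounded figures, in percentage points.

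**Step 3: reading the table.** Within one method, the change of alpha costs 9.9 points at 95% and 6.6 points at 97% for Farrington-Manning (77.5 − 67.6; 90.3 − 83.7), and 9.1 and 5.2 points for Newcombe (79.3 − 70.2; 93.3 − 88.1). The loss is therefore not a product of the formula. The last column is the one that matters to the sponsor, because it compares the basis printed in SAP 5.5 with the rule that will be applied. That gap is smaller because, at the same alpha, the Newcombe rule has somewhat more power here than Farrington-Manning predicts.

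**Step 4: type I error of the planned rule.** Exact enumeration with the vYF rate set 5 points below control gives 2.7%, 2.8%, 2.6% and 1.8% at control rates of 95%, 97%, 99% and 99.9%.

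**The case against.** **The printed 5% may be a remnant of 2.5%.** Several figures in this part of SAP 5.5 are blacked out. In the line after the alpha, the margin has gone without even a block symbol, and the Protocol's alpha is removed altogether. On the other side, the other removed figures in SAP 5.5 leave no digit behind, and the alpha line is the only assumption with a readable number. Partial redaction cannot be excluded. This objection stands as a condition on the point.

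**No printed power figure is shown to be false.** This also stands. The power is stated as an inequality, and it could hold at one-sided 2.5% too.

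**The practical gap is small at high rates.** This stands from 98% upward. The protocol's only prior data, from VYF01 (Protocol 2.1), show 100% seroconversion in YF-naïve participants at a stricter cut-off of 40. That study vaccinated only 72 people across four groups and does not reveal the rate assumed here, but it gives no support for the low end of the range.

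**Stronger readings that a reader might infer.**
- *The test runs at 5%.* It does not. Every statement of the decision rule uses the 95% interval, and its exact error stays near 2.5%.
- *The trial is underpowered or needs more participants.* This cannot be shown while the target power and the assumed rate are hidden.
- *The 570 and 456 in SAP 5.5 are errors because SAP 5.7 concedes a shortfall* ("Considering that the planned sample size was likely to be not reached"). They are not. SAP 5.5 records the plan, while SAP 5.7 discloses the change and its mitigation, a wider D29 window intended to protect the evaluable number. The documents give no revised evaluable number from which a lower power could be computed.

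**Conclusion.** Wrong as written, of moderate severity, subject to the unredacted text confirming 5%. The level in SAP 5.5 is twice the one-sided level of the decision rule, and nothing in either document reconciles them. The inconsistency does not depend on any assumption. Its size does: it assumes equal true rates, a 5-point margin, 304 and 152 evaluable, and a common rate between 95% and 99%. Measured against the planned Newcombe rule, the overstatement is material up to an assumed rate of about 96% to 97%. The defect is confined to the power justification and does not touch the validity of the non-inferiority conclusion.

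**What to change.** 1. Check the alpha in the unredacted SAP 5.5. If it is 2.5%, no change is needed.
2. If it is 5%, replace it with one-sided 2.5%, and do the same in Protocol 9.2 if that section carries the same figure.
3. Restate the power at 456 evaluable (304 and 152) and the assumed rate for the rule that will be applied: two-sided 95% Newcombe interval, 5-point margin. If the Farrington-Manning figure is kept beside it, give it at one-sided 2.5% and say that it is an approximation.
4. Leave the decision rule and the sample size unchanged.

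The cost is a sentence or two and one recalculation. The stated power may be slightly less favourable. No participants, visits or analyses are added.
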